**Table 6: Statistical Power for Treatment Difference in ACR 20 Response at Week 24**

Sample size per arm Guselkumab/Placebo	ACR 20 Response Rate			Power
	Placebo Group	Guselkumab Group	Difference ( $\Delta$ )	
250/350	35%	55%	20%	>99%
250/350	35%	60%	25%	>99%
250/350	35%	65%	30%	>99%
350/350	35%	55%	20%	>99%
350/350	35%	60%	25%	>99%
350/350	35%	65%	30%	>99%

### 9.2.2. Key Major Secondary Endpoint – Change from Baseline in Modified vdH-S Score at Week 24

For change from baseline in modified vdH-S score, participants in each treatment group can be considered a mixture of two subpopulations: one subpopulation (Spop 1) with a change score of 0 regardless of treatment and another subpopulation (Spop2) with a change score sampled from a normal distribution. Therefore, the distribution of the vdH-S change scores is determined by 3 parameters: the probability that a participant has a change score of 0, the mean of the normal distribution, and the standard deviation (SD) of the normal distribution. The overall mean (ie, crude mean) of the change scores for a treatment group is the overall average of the change scores among all participants (including both Spops 1 and 2) in that treatment group.

In the PSA3002 study, the following statistics were observed for change from baseline in modified vdH-S score at Week 24 for each treatment group:

The overall mean (SD) of change from baseline in modified vdH-S score at Week 24 was 0.90 (3.14), 0.25 (2.52), and 0.45 (2.38) respectively, for the placebo, guselkumab 100 mg q4w, and guselkumab 100 mg q8w treatment groups. The assumptions for power calculations in this study are based in part on these data, adjusted for the difference in enrichment criteria between studies.

For this study, assuming an overall mean (SD) of change from baseline in modified vdH-S score as 1.13 (3.2), 0.25 (3.1), and 0.45 (3.1) respectively in the placebo, guselkumab 100 mg q4w, and guselkumab 100 mg q8w groups, a sample size of 350/250/350 participants (ie, 7:5:7 ratio, 950 in total) will provide a power of at least 90% and 80% to detect a significant treatment difference at a 2-sided significance level of  $\alpha=0.05$  for guselkumab q4w vs placebo and guselkumab q8w vs placebo comparisons respectively.

**Table 7** provides the statistical power for guselkumab 100mg q4w vs placebo under various assumptions, where the sample size is 250 in the guselkumab group and 350 in the placebo group.

**Table 7: Statistical Power for Treatment Difference in Modified vdH-S Change from Baseline at Week24 for Guselkumab 100mg q4w vs Placebo (N=250, 350)**

Percent Participant with extra 0 (Spop 1)	Normal Placebo (Spop 2)		Normal Guselkumab (Spop 2)		Overall Placebo		Overall Guselkumab		Overall Mean Difference	Power
	Mean	SD	Mean	SD	Mean	SD	Mean	SD		
15%	1.33	3.4	0.29	3.4	1.13	3.2	0.25	3.1	-0.88	92
15%	1.33	3.4	0.34	3.4	1.13	3.2	0.29	3.1	-0.84	89
15%	1.33	3.0	0.29	3.0	1.13	2.8	0.25	2.8	-0.88	96
15%	1.33	3.0	0.34	3.0	1.13	2.8	0.29	2.8	-0.84	95
25%	1.33	3.4	0.29	3.4	1.00	3.0	0.22	2.9	-0.78	87
25%	1.33	3.4	0.34	3.4	1.00	3.0	0.26	2.9	-0.74	83
25%	1.33	3.0	0.29	3.0	1.00	2.7	0.22	2.6	-0.78	94
25%	1.33	3.0	0.34	3.0	1.00	2.7	0.26	2.6	-0.74	91

**Table 8** provides the statistical power for guselkumab 100mg q8w vs placebo under various assumptions, where the sample size is 350 in each group.

**Table 8: Statistical Power for Treatment Difference in Modified vdH-S Change from Baseline at Week 24 for Guselkumab 100mg q8w vs Placebo (N=350, 350)**

Percent Participant with extra 0 (Spop 1)	Normal Placebo (Spop 2)		Normal Guselkumab (Spop 2)		Overall Placebo		Overall Guselkumab		Overall Mean Difference	Power
	Mean	SD	Mean	SD	Mean	SD	Mean	SD		
15%	1.33	3.4	0.53	3.4	1.13	3.2	0.45	3.1	-0.68	80
15%	1.33	3.4	0.58	3.4	1.13	3.2	0.49	3.1	-0.64	75
15%	1.33	3.0	0.53	3.0	1.13	2.8	0.45	2.8	-0.68	89
15%	1.33	3.0	0.58	3.0	1.13	2.8	0.49	2.8	-0.64	84
25%	1.33	3.4	0.53	3.4	1.00	3.0	0.40	3.0	-0.60	74
25%	1.33	3.4	0.58	3.4	1.00	3.0	0.44	3.0	-0.56	69
25%	1.33	3.0	0.53	3.0	1.00	2.7	0.40	2.6	-0.60	84
25%	1.33	3.0	0.58	3.0	1.00	2.7	0.44	2.6	-0.56	79

The statistical power for each comparison was estimated based on 10000 simulations with treatment comparison performed at each simulation using an analysis of variance (ANOVA) test on the van der Waerden normal score. Under these assumptions, the power ranges approximately

from 83% to 96% for the guselkumab q4w vs placebo comparison, and from 69% to 89% for the guselkumab q8w vs placebo comparison.

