### 2.2.1.1. Phase 3 Studies: CINTO1959PSA3001 and CINTO1959PSA3002

#### 2.2.1.1.1. Study design

PSA3001 and PSA3002 had similar study designs. Some differences in study population, sample size, and study duration, reflected the additional study objective in PSA3002 to assess the efficacy of guselkumab on the inhibition of progression of radiographic structural damage.

The completed PSA3001 and ongoing PSA3002 studies are global, multicenter, randomized, double-blind, placebo-controlled, 3-arm studies of guselkumab in participants with active PsA who had inadequate response to standard therapies (eg, non-biologic DMARDs, apremilast, or nonsteroidal anti-inflammatory drugs [NSAIDs]). Both studies included a screening phase of up to 6 weeks and a treatment period including a placebo-controlled period from Week 0 to Week 24, and both have an active treatment period that began at Week 24 and a safety follow-up period of 12 weeks after the last administration of study treatment. Stable doses of concomitant NSAIDs, oral corticosteroids, and selected DMARDs (limited to methotrexate [MTX], sulfasalazine [SSZ], hydroxychloroquine [HCQ], and leflunomide [LEF]) were allowed but not required.

The PSA3001 study allowed approximately 30% of participants who had prior exposure to anti-tumor necrosis factor (TNF)- $\alpha$  agents to enroll, ie, participants who had been previously treated with up to 2 anti-TNF $\alpha$  agents. In the PSA3002 study, participants were required to be naïve to biologic agents. A higher C-reactive protein (CRP) and joint count was requirement for enrollment in PSA3002, listed below, which was intended to enrich the population for participants at greater risk for structural damage progression so that the impact of guselkumab on radiographic parameters could be assessed:

- **PSA3001:**  $\geq 3$  swollen joints and  $\geq 3$  tender joints at screening and baseline, and CRP  $\geq 0.3$  mg/dL at screening
- **PSA3002:**  $\geq 5$  swollen joints and  $\geq 5$  or more tender joints at screening and baseline, and CRP  $\geq 0.6$  mg/dL at screening

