In addition to clinical signs and symptoms, an important outcome in PsA is inhibition of structural damage. Analyses of radiographic data in PSA3002 demonstrated that the guselkumab 100 mg q4w dose regimen significantly inhibited structural damage progression compared with placebo. While structural damage progression was numerically lower for the guselkumab 100 mg q8w dose regimen compared with placebo, it did not reach statistical significance. Since many patients with PsA do not experience joint damage (approximately two thirds of the participants in PSA3002 did not progress regardless of treatment group), additional analyses were conducted to identify risk factors that predicted which participants are at increased risk of structural damage progression. Risk factor analyses using placebo data from previous Sponsor-conducted PsA studies with other therapeutic agents identified the number of joints with erosion as the baseline risk factor most predictive for an increased risk of structural damage progression. In high-risk participants (ie, those with baseline risk factors), while both guselkumab dose regimens had less structural damage progression than placebo, there appeared to be a dose response trend with the guselkumab 100 mg q4w dose regimen showing greater benefit than the 100 mg q8w dose regimen in inhibiting structural damage progression.

Overall, the two proposed dose regimens demonstrated clinically meaningful efficacy and were well tolerated with an acceptable safety profile in participants with active PsA. This study is expected to provide additional clinical safety and efficacy data (especially for the evaluation of inhibition of structural damage) in participants with PsA. Inclusion of both the 100 mg at Week 0 and 4 and then q8w dose regimen and the 100 mg q4w dose regimen will allow a relative benefit-risk assessment of the q4w dose regimen.

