##### **5.1. Inclusion Criteria**

Each potential participant must satisfy all of the following criteria to be enrolled in the study:

1. Be at least 18 years of age (or the legal age of consent in the jurisdiction in which the study is taking place).
2. Have active PsA despite previous non-biologic DMARD, apremilast, and/or NSAID therapy.

- Non-biologic DMARD therapy is defined as taking a non-biologic DMARD for at least 3 months or evidence of intolerance.
- Apremilast therapy is defined as taking apremilast at the marketed dose approved in the country where the study is being conducted for at least 3 months or evidence of intolerance.
- NSAID therapy is defined as taking an NSAID for at least 4 weeks or evidence of intolerance.

3. Have a diagnosis of PsA for at least 6 months prior to the first administration of study intervention and meet ClASsification criteria for Psoriatic ARthritis (CASPAR) criteria at screening.

4. Criterion modified per Amendment 1

4.1. Have active PsA as defined by:

- a. At least three swollen joints and three tender joints at screening and at baseline
  - AND-
  - b. CRP  $\geq 0.3$  mg/dL at screening from the central laboratory.

**NOTE:** A one-time repeat assessment of CRP level is allowed during the 6-week screening phase and the investigator may consider the participant eligible if the test result is within acceptable range on repeat testing in the central laboratory.

5. Have  $\geq 2$  joints with erosions on baseline radiographs of the hands and feet as determined by central read.

6. Have at least one of the following PsA subsets: distal interphalangeal joint involvement, polyarticular arthritis with absence of rheumatoid nodules, asymmetric peripheral arthritis, or spondylitis with peripheral arthritis.

7. Have active plaque psoriasis, with at least one psoriatic plaque of  $\geq 2$ cm diameter and/or nail changes consistent with psoriasis.

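### Is the stated 80% radiographic power for q8w wrong because only the placebo mean was raised for enrichment?

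*Protocol*

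**What the plan says.** Protocol 9.2.2 and SAP 3.1.2 carry the same text. They report the PSA3002 Week 24 changes in modified vdH-S score as "0.90 (3.14), 0.25 (2.52), and 0.45 (2.38) respectively, for the placebo, guselkumab 100 mg q4w, and guselkumab 100 mg q8w treatment groups", and say the planning values rest in part on these data, "adjusted for the difference in enrichment criteria between studies". The power is then computed "assuming an overall mean (SD) of change from baseline in modified vdH-S score as 1.13 (3.2), 0.25 (3.1), and 0.45 (3.1) respectively" for placebo, q4w and q8w. On that basis, "a sample size of 350/250/350 participants (ie, 7:5:7 ratio, 950 in total) will provide a power of at least 90% and 80" per cent for q4w and q8w against placebo.

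The model mixes exact zeros (Spop 1, 15% or 25%) with a normal component (Spop 2). Power was simulated with an ANOVA on van der Waerden scores, each comparison taken individually. Protocol Tables 7 and 8 (SAP Tables 4 and 5) vary the share of zeros, the SD and the guselkumab mean. The summary range for the weaker comparison is "from 69% to 89% for the guselkumab q8w vs placebo comparison".

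**The concern.** An enrichment adjustment would be expected to act on every arm. Here the placebo mean rises by 26% (1.13/0.90 = 1.256) and both guselkumab means stay at their PSA3002 values. The assumed effect is therefore larger than the one PSA3002 showed, in difference and in ratio, and no reason is given. It amounts to assuming that both regimens prevent all the extra progression that enrichment brings.

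Two other passages seem to sharpen the point. Protocol 4.3 says that in high-risk participants "there appeared to be a dose response trend with the guselkumab 100 mg q4w dose regimen showing greater benefit than the 100 mg q8w" regimen, which gives no support for a q8w gain under enrichment. The direction of the enrichment is also mixed. Of the earlier trial, Protocol 2.2.1.1.1 says: "A higher C-reactive protein (CRP) and joint count was requirement for enrollment in PSA3002, listed below, which was intended to enrich the population". The present trial relaxes both criteria, to CRP of at least 0.3 rather than 0.6 mg/dL and to "At least three swollen joints and three tender joints at screening and at baseline" rather than five of each, while adding the requirement for at least two eroded joints.

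Protocol 2.1 notes that only q4w reached significance on this endpoint in PSA3002, and 4.2 says the present trial is to investigate both regimens further. If q8w power were really near two in three, a second non-significant q8w result would be quite likely even with the PSA3002 inhibition, and a reader told 80% could misjudge it.

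**Working it through.** **Inputs.** Means, SDs, sample sizes and mixture parameters come from Protocol 9.2.2 and Tables 7 and 8. Alpha is 0.05 two-sided.

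**1. Reproduce the stated power.** In the base case (15% zeros, Spop 2 SD 3.4), the overall means are 0.85 × 1.33 = 1.13, 0.85 × 0.53 = 0.45 and 0.85 × 0.29 = 0.25. Simulating the mixture with the van der Waerden test gives 80.6% for q8w (stated 80%) and 92.3% for q4w (stated 92%). All eight rows of Table 8, and the four rows of Table 7 that were rerun, agree within 2 points. A normal approximation agrees for q8w:

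- SE = √((3.2² + 3.1²)/350) = 0.238
- power = Φ(0.68/0.238 − 1.96) ≈ 81%

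**2. Implied inhibition (1 − guselkumab mean / placebo mean).**

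| | PSA3002 | Plan | Range over table rows |
|---|---|---|---|
| q8w | 1 − 0.45/0.90 = 50% | 1 − 0.45/1.13 = 60% | 56% to 60% |
| q4w | 1 − 0.25/0.90 = 72% | 1 − 0.25/1.13 = 78% | 74% to 78% |

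No row sits at the PSA3002 inhibition.

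**3. Alternative: keep PSA3002 inhibition against a placebo mean of 1.13.** The q8w mean is 1.13 × 0.50 = 0.565, a difference of 0.565. The q4w mean is 1.13 × 0.25/0.90 = 0.314, a difference of 0.816. With the plan's base-case zeros and SD, simulated power is 66.0% for q8w and 86.9% for q4w. Over the four zero/SD settings used in the tables, q8w runs from 59% to 76%.

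**4. Same alternative with PSA3002 SDs.** Step 3 replaces the plan's means but keeps its SDs, which were raised from 2.38 to 3.1 for q8w and from 2.52 to 3.1 for q4w. Taking means and SDs from the same source:

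- q8w: SE = √((3.14² + 2.38²)/350) = 0.211; power = Φ(0.565/0.211 − 1.96) ≈ 77%
- q4w: SE = √(3.14²/350 + 2.52²/250) = 0.231; power = Φ(0.816/0.231 − 1.96) ≈ 94%
- The plan's own q8w difference with these SDs: Φ(0.68/0.211 − 1.96) ≈ 90%

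So the SD choice costs the plan roughly 8 to 11 points of q8w power (90% against 81%; 77% against 66%), and the mean choice gains about 14.

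**5. What Table 8 already shows.** The eight q8w powers are 80, 75, 89, 84, 74, 69, 84 and 79. Four are below 80%. Two rows have a difference of 0.56, with power 69% and 79%. Those rows reach 0.56 by having more zeros, so their overall SDs are smaller (2.6 to 3.0) and their inhibition is 56%. They are close to the alternative in difference but not in ratio.

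**6. Cost of 80% at a difference of 0.565.** Per arm, n = 2 × (1.96 + 0.84)² × 3.15² / 0.565² ≈ 488, against 350. Enlarging only placebo and q8w means 2 × 138 = 276 more participants.

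**The case for a change.** The case for acting is that 50% is the only q8w inhibition this sponsor's trial evidence shows, and no table row uses it. Even with PSA3002 SDs, q8w stays a few points under 80%. If enrichment brought no gain at all (difference 0.45, PSA3002 SDs), q8w power would be Φ(0.45/0.211 − 1.96) ≈ 57%. H4 is also tested last in a fixed sequence, so its chance of success is somewhat below its marginal power. A subset summary of PSA3002 participants with at least two eroded joints would settle the inputs cheaply.

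It stands that the derivation of 1.13 is not given, that the unchanged guselkumab means are not justified, and that a 50% row is absent. The rest carries less weight:

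- The adjustment was not confined to one arm. The guselkumab SDs rose by 23% and 30% (3.1/2.52 and 3.1/2.38), in the conservative direction.
- Protocol 4.3 compares q4w with q8w among high-risk participants. It does not say that q8w inhibits less there than in the whole PSA3002 population, and the planning means already give q4w the advantage. The same sentence says both regimens progressed less than placebo.
- Protocol 4.3 also describes risk-factor analyses on placebo data from other sponsor studies. These could underlie a placebo-only shift, though the documents do not make the link.
- The planned test is an ANCOVA on multiply imputed data, adjusted for baseline score and strata (SAP 5.3.5.1.3). Neither 80% nor 66% is exactly its power.

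**Conclusion.** No change to the plan. The 80% and 92% follow from the inputs printed beside them. The figures of 66% for q8w and 87% for q4w hold only if proportional inhibition is constant across risk levels and the plan's larger SDs are kept. With PSA3002 SDs they become about 77% and 94%. If progression on q8w stays near 0.45 in the enriched population, 80% stands. The documents cannot decide between these, and statisticians would reasonably differ.

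Explaining 1.13 and adding a table row would improve the account of the sample size but change nothing that is computed from the trial. H1 alone decides whether the study is positive (SAP 2). H4 comes last in the sequence, so low power there affects no other test and no error rate. A non-significant q8w result would be read from its estimate and confidence interval, and a reader is already told that q8w power may be as low as 69%. Enrolling at least 276 more participants to secure 80% under one alternative is a choice about resources. It does not correct an error.

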### 9.3. Populations for Analysis Sets

For the purpose of various analyses, the following populations are defined.

Population	Description
Enrolled	All participants who signed the informed consent form (ICF).
Full Analysis Set	All participants who were randomized in the study. This analysis set will be used for the efficacy analyses.
Modified Full Analysis Set	All participants who were randomized, excluding participants from sites rendered unable to support key study operations due to a Natural Disaster or Major Disruption. Details will be provided in the SAP.
Safety Analysis Set	All participants who received at least one (complete or partial) administration of study intervention, ie, the treated population.
Immunogenicity Analysis Set (IAS)	All participants who received at least one (complete or partial) administration of guselkumab and who had at least 1 sample obtained after their first administration of guselkumab.
PK Analysis Set (PKAS)	All participants who received at least one complete administration of guselkumab and had at least valid blood sample drawn for PK analysis.
PD Analysis Set (PDAS)	All participants who received at least one (complete or partial) administration of study intervention.

### 9.4. Statistical Analyses

The SAP will be finalized prior to DBL and it will include a more technical and detailed description of the statistical analyses described in this section. This section is a summary of the planned statistical analyses of the most important endpoints including primary and key secondary endpoints.

#### 9.4.1. General Considerations

In general, descriptive statistics, such as mean, SD, median, inter quartile range, minimum, and maximum for continuous variables, and counts and percentages for discrete variables will be used to summarize most data.

For binary response efficacy endpoints, treatment comparisons will generally be performed using a Chi-square test or a Cochran-Mantel-Haenszel (CMH) test. For continuous endpoint of efficacy data, treatment comparisons will be performed using an analysis of covariance (ANCOVA), a mixed model for repeated measures (MMRM) model or a constrained longitudinal data analysis (cLDA) Model.

In general, statistical testing will be performed using 2-sided tests. The overall type I error will be controlled among the primary and major secondary endpoints at 5%.

#### 9.4.2. Primary Endpoint

The primary endpoint is the proportion of participants who achieved an ACR 20 response at Week 24. The primary analysis of this endpoint will be based on the **adjusted composite estimand** defined by the 5 components:

- Population: Participants with active PsA who are biologic naïve, and were randomized and treated with study intervention
- Treatment:
  - Placebo
  - Guselkumab
- Variable: ACR20 composite binary response variable at Week 24, where a responder is defined as a participant who achieves ACR20 response at Week 24 and does not experience ICE categories 1 to 3.
- Intercurrent Events: ICE categories 1 to 3 will follow the composite strategy, where participants who meet them prior to Week 24 will be considered as treatment failures and will be treated as non-responders regardless of the observed ACR20 response status. The ICE categories 4 and 5 will follow the hypothetical strategy postulating a scenario where a Natural Disaster (eg, the COVID-19 pandemic) as well as Major Disruption (eg, the disruption involving Ukraine and neighboring countries/territories beginning 24 February 2022; specific details to be included in the SAP), and ICEs directly resulting from them, did not occur, and observed data through Week 24 after meeting these ICEs will not be used and will be assumed to be MAR. For participants experiencing multiple ICEs, an ICE in categories 1 to 3 will supersede an ICE in categories 4 and 5.
  1. Discontinued study intervention injections due to any reason **except** due to a Natural Disaster or Major Disruption.
  2. Initiated or increased the dose of non-biologic DMARDs (MTX, SSZ, HCQ, LEF) or oral corticosteroids over baseline for PsA.
  3. Initiated protocol prohibited medications/therapies for PsA.
  4. Discontinued study intervention injections due to a Natural Disaster or Major Disruption.
  5. Severe treatment non-compliance (to be defined in the SAP) due to a Natural Disaster or Major Disruption.
- Population level summary: difference in proportion of responders between guselkumab group and placebo group.

Data from all participants in the mFAS-will be analyzed according to randomized treatment group regardless of the treatment actually received. Participants with missing data for any reason other than due to a Natural Disaster or Major Disruption will be considered non-responders, while missing data due to a Natural Disaster or Major Disruption or data not used due to ICE categories 4 or 5 will be assumed to be MAR and imputed using MI. For each guselkumab dose versus placebo comparison, a CMH test stratified by the randomization strata levels will be conducted for each imputation set, and the Wilson-Hilferty transformation will be applied to the CMH statistics across the imputation sets before combining them for the final p-values. The magnitude of the effect will be estimated by the difference in ACR 20 response rates between the guselkumab and placebo groups with the 95% confidence interval calculated based on Wald statistics.

To evaluate the robustness of the primary endpoint analysis results, the exhaustive scenario tipping point sensitivity analyses will be performed by varying the amount of non-responder imputation for missing data.

Additional sensitivity/supplemental analyses which vary how intercurrent events (eg, alternative estimand) are handled, how observed data are used, and how missing data are treated will be specified in the SAP to further address the robustness of treatment effect of ACR 20 at Week 24.

